9.6 Safety Review Team

The project's SRT includes as core members the GSK Biologicals' Central Safety Leader, the CRDL, Epidemiologist, Global Regulatory Lead and a Biostatistician of the project. The SRT is responsible for ongoing safety monitoring of the entire project and meets on a regular basis. The SRT will inform the iSRC about any potential safety concern relevant to the study (in a blinded way).

Before each iSRC safety evaluation in this study (see below), the SRT will review the same safety data, but in a blinded manner in order to keep all people involved in the conduct, cleaning and final analysis of the study blinded.

9.7 Internal Safety Review Committee

As the investigational vaccine formulation will be administered to human for the first time, an iSRC will be appointed in addition to the project's existing SRT and safety holding rules have been defined.

This study will be overseen by an iSRC operating under a charter. Core members of the iSRC will include a GSK safety physician, a CRDL/CEPL, and a biostatistician who are not otherwise involved in the conduct of the project. The iSRC safety reviews will be conducted using unblinded data. Upon request, the iSRC has access to the subject randomization and reviews unblinded data.

In Steps 1, 2, and 3, the iSRC will review all accumulating safety data after Dose 1 and then again after Dose 2, and in Step 4 the iSRC will review all accumulating safety data 3 weeks after the start of vaccination in Step 4 and then about every 3 weeks until all subjects have received Dose 1. If there are any safety concerns observed during SRT reviews post Dose 3, an ad hoc iSRC meeting will take place to review the unblinded safety data.

The iSRC members will determine whether any of the predefined holding rules are met (refer to Section 4.6.1) or if there is any other safety signal. In this case, administration of the second vaccination will be immediately put on hold (refer to Section 4.6.2). If no safety signal is observed, the second vaccination will be administered to the subjects. At the end of each step, the iSRC will review all safety data from the entire step. The iSRC members will determine whether any of the predefined holding rules are met (refer to Section 4.6.1) or if there is any other safety signal. In this case, vaccination in the next step will be put on hold (refer to Section 4.6.2). If no safety signal is observed, vaccination in the next step will be performed (refer to [Figure 1](#)).

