- **Step 3:** Vaccination of approximately 30 subjects aged 50-70 years (approximately 10 subjects in the CDIFF Ag group, approximately 10 subjects in the CDIFF Ag + an adjuvant system containing 3-O-desacyl-4'-monophosphoryl lipid A [MPL], QS-21 and liposome [50 µg MPL and 50 µg QS-21] AS01B group, and approximately 10 subjects in the placebo group). An iSRC will review all accumulating safety data after Dose 1, and then after Dose 2. Vaccination in Step 4 will proceed in the absence of a safety concern detected by the iSRC on all accumulating safety data at the end of Step 3.

- **Step 4:** Vaccination of approximately 70 subjects aged 50-70 years (approximately 25 subjects in the CDIFF Ag group, approximately 35 subjects in the CDIFF Ag + AS01_B group, and approximately 10 subjects in the placebo group). An iSRC will review all accumulating safety data 3 weeks after the start of vaccination in Step 4 and then about every 3 weeks until all subjects have received Dose 1. In addition, the iSRC will review all safety data after Dose 2 (refer to Section 8.11 for study procedures to be considered during special circumstances). A subcohort of subjects who have successfully completed all visits up to Visit 7, have received two doses on an active arm (ie, the subjects who received placebo will be excluded), do not meet any contraindication for subsequent vaccination, and still meet the eligibility criteria will receive a third dose after the iSRC has reviewed all the accumulating safety data at the end of Step 4 Dose 2. If there are any safety concerns observed during SRT reviews post Dose 3, an ad hoc iSRC meeting will take place to review the unblinded safety data.

Refer to Section 9.6 for iSRC oversight.

During all 4 steps, all subjects should be closely observed for at least 60 minutes after vaccination.

For Steps 1, 2, and 3 only, all subjects should be vaccinated sequentially and at least 60 minutes apart to allow for monitoring of any acute events (eg, hypersensitivity reaction).

During vaccination days of Steps 1, 2, and 3 (ie, Day 1 and Day 31), vaccination will be limited to a maximum of 10 subjects per day. In Step 4, there is no limit related to the number of subjects to be vaccinated per day.

Table 10 Study Groups Foreseen in the Study (Refer to Section 8.11 for Study Procedures to be Considered During Special Circumstances)

Step	Study Groups	Number of Subjects	Age (Minimum/Maximum)
1	Placebo	10	18-45 years
	CDIFF Ag	10	18-45 years

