4.2 Scientific Rationale for Study Design

4.2.1 Rationale for Study Blinding

Given the different appearance of the *C. difficile* investigational vaccines and placebo, double blinding is not possible, and the study will be conducted in an observer-blind manner. In an observer-blind study, the subject, the Contract Research Organization personnel, and the study center and Sponsor personnel involved in the clinical evaluation of the subjects are blinded while other study personnel may be aware of the treatment assignment.

When all data up to Day 61 are available, a statistical analysis will be performed (first interim analysis). The immunogenicity data available until Day 61, and the safety and reactogenicity data available at the time of this analysis will be described. At this point, the statistician will be unblinded for the analysis (ie, will have access to individual subject treatment assignments). The remaining study personnel will stay blinded (ie, will not have access to the individual subject treatment assignment) until study end. It is possible however, due to the limited sample size, that unblinding occurs for a few subjects having a specific adverse event (AE) or serious adverse event (SAE) (eg, an AE/SAE occurring only in a single group). Therefore, anyone having access to the analysis of Day 61 could become unblinded regarding those specific cases. The study will be considered as partial blind from this point onwards.

The third dose will be administered to the Step 4 subjects who received the active components, in a partial blind manner. The Investigator and the subjects will not have access to the treatment allocation up to study end (Day 390). After Day 390, only the subjects will remain fully blinded, while the Investigator will be partially blinded, as no placebo subjects will be included for Dose 3.

Please refer to [Appendix 2](#) for the definition of observer-blind and partial blind.

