4.3 Justification for Dose

The F2 candidate antigen developed by GSK contains a portion of the amino acids sequence of the full-length *C. difficile* toxins. Another manufacturer developing a *C. difficile* vaccine based on the use of genetically detoxified full-length Toxin A and Toxin B, reported optimal immunogenicity data at a dose of 100 µg each (clinical trial: NCT01706367). The proposed dose of F2 antigen is defined to obtain an equivalent number of epitopes (included in F2 sequence) as reported in the Phase I study.

Moreover, findings from the repeated dose toxicology study indicate that the investigational vaccine F2/AS01_B was well tolerated when administered three times at two-week intervals. No safety risks were identified. Please refer to the current IB for more information regarding the preclinical studies of *C. difficile* investigational vaccine (GSK2904545A).

In addition to these observations, pooled analyzes of AS01 adjuvanted vaccines in humans yielded that there is no safety concern for the administration of the same AS01 adjuvanted vaccine. Increase of reactogenicity is expected after dose 2 or dose 3 of the same adjuvanted vaccine.

Based on these data, it is recognized that CDIFF F2 AS01_B has an acceptable safety profile (reactogenicity).

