4.6 Study Holding Criteria

4.6.1 Study Holding Rules

The safety holding rules which will be assessed by the Investigator are defined in [Table 11](#) and the safety holding rules which will be assessed by the iSRC are defined in [Table 12](#). The toxicity grading scales for hematology, biochemistry, and urinalysis parameters applicable for this study are presented in [Table 13](#).

Table 11 Holding Rules Assessed by the Investigator

Holding Rule	Event	Number of Subjects
1a	Death or any life-threatening SAE.	≥1
1b	Any withdrawal from the study following a Grade 3 AE that cannot reasonably be attributed to a cause other than vaccination.	≥1
1c	Any SAE or fever >40°C (104°F) that cannot reasonably be attributed to a cause other than vaccination, or visible necrosis at the injection site, within the 7-day (Day 1 to Day 7) period after vaccination.	≥1

AE = adverse event; SAE = serious adverse event.

Table 12 Holding Rules Assessed During Internal Safety Review Committee Evaluations

Holding Rule	Event	Percentage of Subjects
2a	Any Grade 3 solicited local AE (lasting 48 hours or more) in an investigational group, within the 7-day (Day 1 to Day 7) period after vaccination.	≥20% (per group)
2b	Any Grade 3 solicited general AE (lasting 48 hours or more) in an investigational group, that cannot reasonably be attributed to a cause other than vaccination, within the 7-day (Day 1 to Day 7) period after vaccination.	≥20% (per group)
2c	Any Grade 3 unsolicited AE in an investigational group, that cannot reasonably be attributed to a cause other than vaccination, within the 7-day (Day 1 to Day 7) period after vaccination.	≥20% (per group)
2d	Any Grade 3 abnormality in prespecified hematological or biochemical laboratory parameters in an investigational group within the 7-day (Day 1 to Day 7) period after vaccination (refer to Table 13).	≥20% (per group)

AE = adverse event.

[Figure 2](#) illustrates that, with 10 subjects per group:

- For holding rules 1a, 1b, and 1c, using a cutoff of 1/10, there is more than 80% chance that the holding rule is met for a vaccine with a true incidence rate above 15% and there is more than 60% chance that the holding rule is not met for a vaccine with a true incidence rate below 5%.
Since this holding rule will be assessed on a continuous basis by the Investigator, irrespective of the number of subjects enrolled, the statistical interpretation of this holding rule is less relevant.

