4.6.2 Procedure if the Study is Put on Hold

If the Investigator detects 1 of the holding rules, he/she will immediately put the enrollment or the vaccination on hold and he/she will immediately inform the Sponsor and enter the data in the electronic case report form (eCRF), but all other procedures relating to safety and immunology will continue. In case 1 of the holding rules (1a, 1b, or 1c) is met, the iSRC will meet urgently and review the unblinded data. During this time the study will be kept on hold. The iSRC will inform the study Clinical Research and Development Lead (CRDL) who will inform the relevant bodies of the Sponsor about the outcome of the review and the recommendation on whether to suspend, modify, or continue the conduct of the study on all groups or on selected groups. The decision regarding the further conduct of the study will be documented and provided in writing to the Investigators.

During this review period, the study will be temporarily stopped, while the decision is being made. In case of a decision to stop the study, a letter indicating the reason will be sent to the Institutional Review Board (IRB)/Independent Ethics Committee (IEC) by the Investigator and to the Regulatory Agency by the Sponsor.

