6.1 Study Treatment(s) Administered

Table 14 Description of Study Treatment

Treatment Name	Vaccine Name	Formulation	Presentation	Volume to be Administered	Number of Doses
Placebo	NaCl	NaCl = 150mM	Clear liquid for suspension	0.5 mL	2 doses
CDIFF Ag	F2	F2 antigen	Lyophilized	0.5 mL	2 or 3 doses*
	NaCl	NaCl = 150mM	Clear liquid for suspension		
CDIFF Ag + AS01 _B	F2	F2 antigen	Lyophilized	0.5 mL	2 or 3 doses*
	AS01 _B	MPL = 50 µg; QS-21 = 50 µg; Liposomes	Liquid in a monodose vial		

Ag = antigen; AS01_B = an adjuvant system containing MPL, QS-21 and liposome (50 µg MPL and 50 µg QS-21);

GSK = GlaxoSmithKline Biologicals SA; MPL = 3-O-desacyl-4'-monophosphoryl lipid A; QS-21 = *Quillaja saponaria* Molina, fraction 21 (Licensed by GSK from Antigenics Inc., a wholly owned subsidiary of Agenus Inc., a Delaware, USA corporation)

* *a third dose will be administered to a subcohort of subjects in Step 4*

Table 15 Dosage and Administration of Study Treatment

Type of Contact and Timepoint	Study Group	Treatment Name	Volume to be Administered	Route	Injection Site	
					Location	Laterality ^a
Visit 1 (Day 1)	Placebo	Placebo	0.5 mL	IM	Deltoid	Nondominant
	CDIFF Ag	CDIFF Ag	0.5 mL	IM	Deltoid	Nondominant
	CDIFF Ag + AS01 _B	CDIFF Ag + AS01 _B	0.5 mL	IM	Deltoid	Nondominant
Visit 3 (Day 31)	Placebo	Placebo	0.5 mL	IM	Deltoid	Nondominant
	CDIFF Ag	CDIFF Ag	0.5 mL	IM	Deltoid	Nondominant
	CDIFF Ag + AS01 _B	CDIFF Ag + AS01 _B	0.5 mL	IM	Deltoid	Nondominant
Visit 8 (Day 491)	CDIFF Ag	CDIFF Ag	0.5 mL	IM	Deltoid	Nondominant
	CDIFF Ag + AS01 _B	CDIFF Ag + AS01 _B	0.5 mL	IM	Deltoid	Nondominant

Ag = antigen; AS01_B = an adjuvant system containing MPL, QS-21 and liposome (50 µg MPL and 50 µg QS-21);

IM = intramuscular; MPL = 3-O-desacyl-4'-monophosphoryl lipid A.

^a The nondominant arm is the preferred arm of injection. In case it is not possible to administer the vaccine in the nondominant arm, an injection in the dominant arm may be performed.

For each subject, the Investigator is not permitted to start the administration of the next dose until receipt of the favorable outcome of the safety evaluation, documented and provided in writing (scanned and emailed), authorizing the Investigator to proceed. Moreover, if the Investigator becomes aware of a holding rule being met, he/she will suspend vaccination and will inform GSK immediately (see [Table 11](#) and [Table 12](#)).

Refer to Section [4.6.1](#) for detailed description of holding rules and safety monitoring.

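### Per-group holding rules 2a–2d have no scheduled unblinded evaluation while Dose 3 is being given

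*Protocol*

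**What the plan says.** Table 12 in Protocol 4.6.1 is titled "Holding Rules Assessed During Internal Safety Review Committee Evaluations". Its four rules concern Grade 3 solicited local, solicited general, unsolicited and laboratory events. Each is met at 20% or more of an investigational group within 7 days after vaccination, and none is limited to a particular dose.

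The iSRC calendar is in Protocol 4.1 and 9.7: after Doses 1 and 2 in Steps 1–3, about every 3 weeks during Step 4 Dose 1, and after Step 4 Dose 2. Eligible subjects in the active arms of Step 4 "will receive a third dose after the iSRC has reviewed all the accumulating safety data at the end of Step 4 Dose 2". From then on, Section 9.7 provides: "If there are any safety concerns observed during SRT reviews post Dose 3, an ad hoc iSRC meeting will take place".

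Two other routes stay open. Section 4.6.2 states: "In case 1 of the holding rules (1a, 1b, or 1c) is met, the iSRC will meet urgently and review the unblinded data". Section 6.1 adds that "if the Investigator becomes aware of a holding rule being met, he/she will suspend vaccination". On blinding, Section 9.6 has the SRT work blinded, and Section 4.2.1 says that after Day 390 "the Investigator will be partially blinded, as no placebo subjects will be included for Dose 3".

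**The concern.** The rules are defined per group, but after Dose 3 nobody is scheduled to look at the data per group. The SRT decides whether the iSRC meets, and it is blinded. The Investigator must suspend vaccination on learning that a rule is met, but knows only that no Dose 3 recipient is on placebo, not who has the adjuvant. Rules 1a–1c cover deaths, life-threatening and certain other serious events, withdrawal after a Grade 3 event, very high fever and injection-site necrosis. They do not cover a raised rate of Grade 3 reactions or laboratory abnormalities.

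An excess confined to one formulation is diluted when the two active arms are viewed together. Such an excess is plausible, since Section 4.3 says "Increase of reactogenicity is expected after dose 2 or dose 3 of the same adjuvanted vaccine", although the same section reports no safety concern. What is at stake is whether subjects still waiting for Dose 3 would be vaccinated after a rule had in fact been met.

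**Working it through.** **1. The plan's own figures.** Section 4.6.1 gives, for a cutoff of 2 in 10, more than 80% chance of meeting the rule above a true rate of 27%, and more than 80% chance of not meeting it below 8%. Exact binomial:

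- P(X ≥ 2 | n = 10, p = 0.27) = 1 − 0.73^10 − 10(0.27)(0.73^9) = 0.798
- P(X ≤ 1 | n = 10, p = 0.08) = 0.92^10 + 10(0.08)(0.92^9) = 0.812

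Both reproduce to within rounding.

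**2. Looks at Dose 3 data.**

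| Route | Unblinded, per group? | Scheduled? | In time to hold Dose 3? |
|---|---|---|---|
| iSRC after Step 4 Dose 2 | Yes | Yes | Held before Dose 3, so contains no Dose 3 data |
| Urgent iSRC, rules 1a–1c | Yes | Event-driven | Yes, but not for rules 2a–2d |
| Ad hoc iSRC | Yes | Only if the SRT has a concern | Possibly |
| SRT review | No | Regular | Yes, but blinded |
| End-of-step iSRC review (9.7) | Yes | Yes, if it covers Dose 3 | No, it follows the step |
| Second interim analysis (9.5) | By group, descriptive | Yes | No, it needs all data to Day 521 |

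**3. Dilution.** Step 4 has 35 adjuvanted and 25 antigen-alone subjects, at most 60 for Dose 3. Half of each is 17.5 and 12.5; I assume 18 and 12 dosed, with about 30 waiting. The 20% cutoffs are then 4 of 18 (0.2 × 18 = 3.6) and 3 of 12 (0.2 × 12 = 2.4). A result of 4/18 (22%) with 0/12 meets the rule, yet combined it is 4/30 = 13.3%. In the full cohort, 7/35 (20%) with 0/25 combines to 7/60 = 11.7%.

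**4. Chance that a rule is met and not referred.** Let X ~ Bin(18, pA) for the adjuvanted arm and Y ~ Bin(12, pB) for antigen alone, independent. A rule is met if X ≥ 4 or Y ≥ 3. It is not referred if X + Y falls below the SRT's trigger, which I must assume: 6, 5, 4 or 3 events in 30 for combined rates of 20%, 15%, 12% and 10%.

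| Assumed pA / pB | P(rule met) | Unreferred, 20% | 15% | 12% | 10% |
|---|---|---|---|---|---|
| 25% / 2% | 0.69 | 0.36 | 0.17 | 0.00 | 0 |
| 30% / 2% | 0.84 | 0.32 | 0.13 | 0.00 | 0 |
| 25% / 10% | 0.73 | 0.21 | 0.06 | 0.00 | 0 |
| 30% / 10% | 0.85 | 0.17 | 0.05 | 0.00 | 0 |
| 10% / 2% | 0.10 | 0.09 | 0.06 | 0.00 | 0 |

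The 20% trigger is the loosest sensible one: if neither rule is met, the total is at most 3 + 2 = 5, so 6 of 30 already implies that an arm has reached 20%. A trigger of 3 misses nothing, because no rule can be met with fewer than 3 events.

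**5. Is there time to act?** Table 7 puts Dose 3 screening 20 to 150 days after Visit 7 and Dose 3 itself 1 to 15 days later, so 21 to 165 days after Visit 7. Staggering is possible but not ensured: "In Step 4, there is no limit related to the number of subjects to be vaccinated per day". If all third doses fell within about a week, no 7-day data would arrive in time to protect anyone.

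**6. False holds under a by-arm check.** With 5 subjects in an arm, one event is 20%; at a true rate of 5% this happens with probability 1 − 0.95^5 = 0.23. With 10 subjects two events are needed: 1 − 0.95^10 − 10(0.05)(0.95^9) = 0.09 at a true 5%, and 1 − 0.812 = 0.19 at 8%, per rule and look.

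**The case against.** The case for leaving the plan alone has substance.

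- **The SRT's remit is wide.** It acts on any safety concern, which is broader than Table 12. An SRT that saw 4 or 5 Grade 3 events in 30 healthy volunteers would probably refer them, and even blinded it can work out the worst case for one arm. This stands, and is why the table reaches zero. But it rests on the SRT's judgment, not on the rule the protocol wrote down.
- **Blinded need not mean combined.** The documents do not exclude masked group labels, and SAP 4.3 lets the sponsor's statistical team see allocation when needed. The iSRC can likewise obtain the randomization on request. These are possibilities and permissions, not scheduled checks.
- **Section 9.7 also has the iSRC review the whole of each step at its end.** A reader might therefore reject any gap, or conversely infer that Dose 3 data never reach the iSRC. Neither is secure. Section 4.1 ties the Step 4 review to the end of Dose 2, and the stated consequence is a hold on a next step, which Step 4 does not have. If the sentence does reach Dose 3, the review comes after dosing.
- **Dose 3 recipients are selected and already reviewed.** They have had two doses of the same formulation and are rescreened, and the rationale for Amendment 03 reports an acceptable safety profile. With 35 subjects, an adjuvanted rate of 25% or 30% at Dose 2 would have escaped the rule with probability 0.19 or 0.06. This lowers the prior risk, but does not cover a further rise at Dose 3.
- **The charter is unseen.** SAP 4.1 and 4.2 refer to it, and SAP 1 places the iSRC and SRT analyses in a separate document. Either may already hold the check. This limits the finding to the protocol text.
- **Frequent by-arm looks at very small numbers would cause false holds.** This stands and shapes the fix.

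**Conclusion.** The gap in the protocol text is real: rules 2a–2d apply to any dose, but no unblinded per-group evaluation of them is scheduled while Dose 3 is being given. I find no statement that Table 12 lapses at Dose 3.

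The size is uncertain. The range of 0 to about 0.36 rests on assumed event rates, an assumed 18/12 split and an assumed SRT trigger, and the trigger matters most. A reader might take 0.36 as the risk of a missed breach. The documents do not support that, because it needs an SRT that reacts only at a combined 20%, a level the protocol never sets.

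Nor do they support reading Dose 3 as unmonitored or as known to be unsafe: rules 1a–1c stay active, the SRT keeps reviewing, and an ad hoc iSRC meeting is available. The benefit of closing the gap exists only if third doses are spread over time. On that footing it is a cheap safety improvement worth making, held with medium confidence because the charter has not been seen.

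**What to change.** While Dose 3 vaccination is ongoing, and once about 10 subjects in an active arm have 7-day post-Dose 3 data, have the existing unblinded iSRC biostatistician tabulate rules 2a–2d by arm about every 3 weeks, the interval already used for Step 4 Dose 1. Any rule met goes to the iSRC, which decides on a hold. The SRT stays blinded and the 20% thresholds do not change. The minimum of about 10 matches a group size for which Section 4.6.1 gives operating characteristics.

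Name Dose 3 in the hold wording of Section 9.7, which now mentions only the second vaccination and the next step; Sections 4.6.2 and 6.1 already suspend vaccination in general terms. If Table 12 is not meant to apply to Dose 3, say so instead. If the charter or the separate iSRC/SRT document already provides the check, only the protocol wording needs aligning.

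The cost is protocol and charter wording, a few tabulations by an existing committee, and the false-hold risk in step 6 of the working. A false hold could delay some third doses, and SAP 11.2 lists the interval between doses among the deviations that lead to per-protocol exclusion.
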